Education of Municipality-based Physiotherapists in Managing Chronic Low Back Pain - an Observational Study

Date

March 20th 2023

Ethical committee reference number

S-20222000 - 156

Objective

To investigate potential changes in patient outcomes following an educational intervention aimed at upskilling physiotherapists in individualized bio-psycho-social management of patients with disabling low back pain (dLBP) in municipality rehabilitation settings. Focus will both be on changes in patient reported outcomes as well as changes in clinician behavior. Likewise, the feasibility of implementing such changes within municipality settings will be evaluated

Method

Design

A prospective, observational case-control study

Participants

Patients with dLBP referred to municipality-based rehabilitation from the Spine Centre of Southern Denmark. Eligibility is determined on the following criteria:

Inclusion Criteria:

- Referred to municipality rehabilitation from the Spine Centre of Southern Denmark
- Over 18-65 years
- Speaks and comprehends Danish
- A score over 40 on the Örebro Musculoskeletal Pain Questionnaire
- Low back pain as dominating cause for referral
- Can receive digital mail in E-boks (electronic communication platform)

Exclusion Criteria:

- A current diagnosis of psychiatric illness that precludes participation in rehabilitation
- a neurologic disorder or other disease that may affect the ability to participate in a municipality-based rehabilitation program
- neurological deficits related with radiographically confirmed lumbar spinal stenosis or radicular pain correlating with the clinical presentation
- Recent (within 6 months) history of a stabilizing operation of the low back

Procedures

Data collection:

All demographic information will be collected at baseline. This includes age, gender, weight, smoking (yes/no), diagnosis, duration of symptoms, job status (Working Yes/No. If Yes: normal capacity or reduced capacity because of back pain. If No: Full-time sick-listed because of back pain or sick-listed due to other reasons) if early retirement: due to back pain?), highest completed education beyond elementary school)

Primary Outcome

Roland Morris Disability Questionnaire 3 months after entering the study

Secondary outcomes

- Pain intensity (lower back and leg) 3 months after entering the study with a numeric rating scale (NRS:0-10)
- Örebro Musculoskeletal Pain Questionnaire 3 months after entering the study

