- Self-perceived ability to work (NRS: 0-10) 3 months after entering the study
- Patient satisfaction, 7-point Likert scale 3 months after entering the study

Other Pre-specified Outcome Measures:

- Checklist to determine the competency of clinicians immediately after study completion
- Barriers and facilitators for implementing new knowledge in clinical practice – qualitative interview

3 month follow-up

- Roland Morris Disability Questionnaire at 3 months after discharge
- Pain intensity (lower back and leg) with a numeric rating scale (NRS:0-10)
- Self-perceived ability to work (NRS: 0-10)
- Patient Assessment of Transitions in Healthcare (PATH)
- Patient satisfaction, 7-point Likert scale

Other Pre-specified Outcome Measures:

- Checklist to determine the competency of clinicians and to assess interrater reliability between clinical supervisors
- Barriers and facilitators for implementing new knowledge in clinical practice – qualitative interview

Schedule of procedures and assessments (for a schematic overview, see fig. 1)

1. All participating physiotherapists (N=25) will recruit eligible patients (N=4 each, total N=100) who are asked to fill out project-specific questionnaires (see *procedures*) at the start and at the end of the rehabilitation program.
2. The participating physiotherapists will undergo a 13-day educational intervention (see description below under *intervention*) focusing on management of low back pain within an individualized multidimensional framework.
3. Point 1 is repeated on an additional 100 patients who undergo rehabilitation after the physiotherapists have completed the course
4. Participating physiotherapists will be evaluated on the background of a competency checklist which is scored by clinical supervisors connected to the study. The checklist will be scored after watching a video recording of a patient consultation performed by the physiotherapist in focus. The checklist covers 6 domains: Subjective and objective assessment, cognitive-functional therapy intervention, style of communication, patient's unhelpful pain behavior, and an overall assessment
5. Physiotherapists who demonstrate high and low competency (as determined by the evaluation of competency, point 4) are invited to participate in a semi-structured interview. The interview will explore the physiotherapists' experience of changes in management (if

any) after the educational intervention. This includes challenges, barriers and facilitating factors.

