Statistical analysis will be performed using the appropriate statistical method according to the specific aims investigated. All demographic variables will be presented as means (\pm standard deviations), median [Interquartile range], or ratio (%) depending on type and distribution of data. All primary and secondary outcomes will be analysed using paired tests (parametric or non-parametric based on normality), comparing baseline data and data 3 months after study start.

The sample size calculation is based on the previous findings of Ussing et al (2020)¹ which included a similar population and was conducted in a specialist spine clinic in a secondary setting. Based on these findings, we expect to find a 30% group difference in disability in favor of the post-education group. With a mean of 36 (SD 18) pre-intervention and 28 (SD 18) post-intervention, we expect that N=100 participants in each group will be sufficient to achieve an alpha level of 0.05 with a 0.8 power assuming a 10-15% dropout-out rate.

Ethical considerations

Participation in the study does not imply any risks for the patients. All study related procedures are either clinically indicated or do not come with any risk or harm. The patient needs to spend a little extra time filling out project-specific questionnaires as compared with standard care. The overall burden of participating is outweighed by the potential gain. This study is conducted in full conformance with the principles of the Helsinki Declaration. However, the project falls outside the scope of the ethical committee (regional and national) in Denmark as it falls under quality assurance.

¹ <https://pubmed.ncbi.nlm.nih.gov/32221554/>

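### The study is sized on a difference between two sequential, non-randomised cohorts, but the only named outcome analysis is a paired test with no cohort term and no covariates

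*Combined protocol and SAP*

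**What the plan says.** The Schedule of procedures and assessments, point 1, states: "All participating physiotherapists (N=25) will recruit eligible patients (N=4 each, total N=100"). The physiotherapists then take the course, and point 3 adds: "Point 1 is repeated on an additional 100 patients who undergo rehabilitation after the physiotherapists have completed the course". These are two separate sets of patients, recruited one after the other by the same 25 clinicians. The Design section calls the study observational, and no randomisation is described.

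The sample size paragraph in Statistics is about the contrast between these sets: "we expect to find a 30% group difference in disability in favor of the post-education group", and "we expect that N=100 participants in each group will be sufficient to achieve an alpha level of 0.05 with a 0.8 power".

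The analysis sentence in the same section reads: "All primary and secondary outcomes will be analysed using paired tests (parametric or non-parametric based on normality), comparing baseline data" with the 3-month data. The sentence that opens the section is general: "Statistical analysis will be performed using the appropriate statistical method according to the specific aims investigated". It names no model and no covariate.

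Age, symptom duration, job status and other baseline factors are collected (Procedures, Data collection). The only use stated for them is description: "All demographic variables will be presented as means" or other summaries suited to the data.

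**The concern.** A paired test compares each patient with their own baseline. It answers whether patients change over three months. It does not answer whether patients treated after the course do better than those treated before it, which is the question that the sample size and the stated aim ("To investigate potential changes in patient outcomes following an educational intervention aimed at upskilling physiotherapists") raise. Two separate within-cohort results cannot separate an education effect from natural course or regression to the mean.

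If the cohorts are then set side by side without a planned model, any difference in who was enrolled in each period enters the comparison. In a non-randomised study, covariates chosen after the data are seen also add analyst discretion. At stake is whether a difference between cohorts can be read as going with the education rather than with the mix of patients.

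**Working it through.** **1. What the study is sized for.** Inputs from Statistics: difference 36 − 28 = 8, SD 18, alpha 0.05 (taken as two-sided), power 0.80, dropout 10–15%.

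n per group = 2 × (1.960 + 0.842)² × 18² / 8² = 79.5, so 80 (81 with the exact t-test). Dividing 80 by 0.90 and 0.85 gives 89 and 95. With 90 or 85 completers per group, power is 0.85 or 0.83. So 100 per group is sufficient for a comparison of two independent groups. A paired test of an 8-point change would need far fewer: about 58, 42 or 26 patients for an assumed baseline-to-3-month correlation r of 0.3, 0.5 or 0.7. The stated N therefore fits a between-cohort contrast.

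**2. What an unadjusted cohort comparison could do.** From the documents: SD 18 (instrument not named, so the points below should not be read as Roland Morris points) and 100 × 0.85 = 85 completers per cohort. Assumed: r = 0.5–0.7, no true education effect, and a baseline lower by d = 2 or 4 points in the post-education cohort.

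- SE of the 3-month difference: 18 × √(2/85) = 2.76
- SE after baseline adjustment: 2.76 × √(1 − r²) = 2.39 (r = 0.5) or 1.97 (r = 0.7)
- False-positive rate for bias b: Φ(−1.96 − b/SE) + 1 − Φ(1.96 − b/SE)

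Condition A: the shift acts only through the baseline score, so the 3-month shift is r × d. Condition B: the cohort difference is stable, so the 3-month shift is d.

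| Condition | d | Unadjusted: bias, false positives | Baseline-adjusted: bias, false positives | Change score: bias |
|---|---|---|---|---|
| A | 2 | 1.0–1.4, 6.5–8% | 0, 5% | 0.6–1.0 against education |
| A | 4 | 2.0–2.8, 11–17% | 0, 5% | 1.2–2.0 against education |
| B | 2 | 2.0, 11% | 0.6–1.0, 6–7% | 0 |
| B | 4 | 4.0, 30.5% | 1.2–2.0, 9–13% | 0 |

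Unadjusted and adjusted biases are towards education. Adjusted bias in B is d × (1 − r); change-score bias in A is −d × (1 − r).

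**3. How large a shift selection could produce.** Assume that a physiotherapist chooses four patients out of m eligible, in one period only, by a criterion correlated 0.3–0.5 with the baseline score. The lowest four of m average 0, 5.23 or 8.59 points below the mean for m = 4, 5 or 6 (SD 18). Multiplied by 0.3–0.5, this gives 0, 1.6–2.6 or 2.6–4.3 points. A 4-point shift needs six eligible referrals and a correlation of at least 4 / 8.59 = 0.47; with five it would need 4 / 5.23 = 0.76. So 2 points is the more representative case and 4 the high end.

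**4. Limit of baseline adjustment.** Suppose instead that the post-education cohort starts 4 points higher but would show no 3-month difference without education. The unadjusted comparison is then unbiased. The adjusted one is biased r × 4 = 2.0–2.8 points towards education, with 13% (r = 0.5) to 29% (r = 0.7) false positives. The advantage of adjustment in the table holds only when baseline and 3-month scores shift in the same direction.

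**The case against.** The strongest reply is that the general sentence on appropriate methods leaves room for a between-cohort, adjusted analysis. It does not exclude one. But it names none, and the specific sentence that covers all primary and secondary outcomes names a different contrast.

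Secondly, both cohorts share one referral source, the same eligibility criteria (including the Örebro threshold) and the same 25 physiotherapists. This stands as a limit on case-mix differences: stable preferences in whom a physiotherapist approaches would largely cancel. It does not cover changes between periods.

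Thirdly, a reader might infer from the missing enrolment rule that physiotherapists will pick more favourable patients after training. The documents do not support that. They do not say how many eligible referrals each physiotherapist sees; with four there is no choice at all. The timeline figure is not shown, so a recruitment detail there cannot be ruled out.

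Fourthly, baseline adjustment is not shown to be best in every case. Change scores are the unbiased analysis under Condition B, and the opposite-direction example reverses the advantage. This stands, and is why the alternatives should be reported beside the adjusted model. The benefit of adding age, symptom duration and job status has not been quantified.

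Finally, the study is labelled observational, its aim is worded cautiously, and measured imbalance would be visible if baseline tables are shown by cohort. That helps interpretation but does not supply the missing contrast.

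**Conclusion.** The point holds for the analysis plan. The study is sized on a between-cohort difference, and the one named outcome analysis does not estimate it and uses no covariates. That rests on the text alone.

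The consequence for the result is possible, not established. The figures depend on an assumed shift, an assumed correlation, 15% dropout and no true effect. The documents do not show that the comparison will be biased, or in which direction. Nor is there an error in the sample size: 100 per group is adequate for its stated inputs. The defect can be corrected by pre-specification, so it should be fixed but is not fatal.

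**What to change.** **Statistics section.** Make the primary analysis a linear regression of Roland Morris score at the primary time point on cohort (pre or post education). Adjust for baseline Roland Morris score, age, symptom duration and job/sick-leave status, all named before data are seen. Include physiotherapist as a random effect, because the same 25 supply both cohorts; a random intercept alone does not capture variation between physiotherapists in the education effect. Report the unadjusted difference and the between-cohort difference in change scores as sensitivity analyses, since together they show how far the result depends on the assumed conditions. Keep the paired tests as within-cohort description.

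**Time point.** Reconcile the timings first. Primary Outcome gives 3 months after entry, Schedule point 1 has questionnaires at the start and end of rehabilitation, and the follow-up list gives 3 months after discharge.

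**Reporting.** Describe the result as an association with the education period, because adjustment covers measured differences only and calendar-time and unmeasured confounding remain.

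Any separate point about the missing between-cohort test should be handled as this same repair.

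**Minor suggestion.** In Schedule points 1 and 3, invite consecutive eligible referrals in each period until four consent, and keep a short log of eligible, invited and declined patients. Its value depends on the unknown number of eligible referrals, which the log would show.

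**Cost.** The analysis and reporting changes are wording only: the covariates are already collected, and a baseline Roland Morris score is implied by the paired test. The enrolment suggestion costs one protocol sentence and a small administrative burden.

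### The pre/post comparison is not held within physiotherapist, so outcome-related loss of physiotherapists after the first phase would bias it

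*Combined protocol and SAP*

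**What the plan says.** Under Schedule of procedures and assessments, point 1 defines the first cohort: "All participating physiotherapists (N=25) will recruit eligible patients (N=4 each, total N=100". Point 2 sends the same group on the course: "The participating physiotherapists will undergo a 13-day educational intervention". Point 3 defines the second cohort: "Point 1 is repeated on an additional 100 patients who undergo rehabilitation after the physiotherapists have completed the course". Read together, these describe one group of 25 physiotherapists, each recruiting 4 patients before and 4 after training.

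The Statistics section sizes the study on a comparison of the two cohorts: "we expect to find a 30% group difference in disability in favor of the post-education group". Its inputs are "With a mean of 36 (SD 18) pre-intervention and 28 (SD 18) post-intervention", and it concludes that "N=100 participants in each group will be sufficient to achieve an alpha level of 0.05 with a 0.8 power", "assuming a 10-15% dropout-out rate". The analysis it describes is paired testing of baseline against 3 months. It names no model for the comparison between cohorts and no physiotherapist term. The legible text does not say what happens if a physiotherapist leaves or does not finish the course.

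**The concern.** There is no concurrent untrained group, so using the same physiotherapists in both phases is a main safeguard for the pre/post contrast. That safeguard is in the recruitment plan but not in the analysis. By the time training starts, a physiotherapist's pre-education patients are already in the study, so later loss can only take away post-education patients. If those lost differ from those who stay in the outcomes their patients achieve, the cohort means differ even when the course does nothing. The dropout allowance is a single rate attached to participants. It does not separately cover the loss of a physiotherapist, which would remove 4 patients at once from one side.

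**Working it through.** **The plan's own figures.** Cohort size: 25 × 4 = 100 per phase, which reproduces. Sample size, with difference 36 − 28 = 8, SD 18, alpha 0.05 (two-sided assumed) and power 0.80: a two-sample t-test needs 81 evaluable per group. That becomes 81/0.90 = 90 at 10% dropout and 81/0.85 = 95.3, rounded up to 96, at 15%. The stated 100 is not exactly reproduced but is sufficient on these inputs. With 85 evaluable per group, power is 82.1%.

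**Size of the bias.** Let k of 25 physiotherapists be missing from the second phase, with equal patients per physiotherapist. Let L and S be the mean 3-month disability for patients of leavers and stayers, with no education effect.

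- Pre-education mean = (k/25)L + (1 − k/25)S
- Post-education mean = S
- Shift in favour of the course = (k/25)(L − S)

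The documents give neither k nor L − S, so both are assumed. Take normally distributed physiotherapist means with SD 18√ICC, and let exactly the k physiotherapists with the worst outcomes leave. By simulation, the mean of the worst k minus the mean of the rest is 1.80 physiotherapist-level SDs at k = 3 and 1.68 at k = 5.

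| Assumed ICC | 18√ICC | k = 3: L − S | k = 3: shift (% of 8) | k = 5: L − S | k = 5: shift (% of 8) |
|---|---|---|---|---|---|
| 0.01 | 1.80 | 3.2 | 0.39 (5%) | 3.0 | 0.60 (8%) |
| 0.05 | 4.02 | 7.2 | 0.87 (11%) | 6.8 | 1.35 (17%) |
| 0.10 | 5.69 | 10.2 | 1.23 (15%) | 9.6 | 1.91 (24%) |

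For example, at ICC 0.01 and k = 3: 3/25 × 3.24 = 0.39. If loss is unrelated to outcome, L − S has expectation zero and so does the shift. If the best physiotherapists leave, the sign reverses.

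**Power of an unadjusted comparison when physiotherapists are lost.** With 85 evaluable before the course, 0.85 × 4 × (25 − k) after it, and clustering ignored: 82.1% at k = 0, 80.5% at k = 2, 79.6% at k = 3 and 77.5% at k = 5. Power is affected little; the issue is bias.

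**Power of a within-physiotherapist comparison.** With physiotherapist as a fixed effect, the residual SD is 18√(1 − ICC) and only physiotherapists with patients in both phases contribute. So n = 0.85 × 4 × (25 − k) per phase, with 2n − (25 − k) − 1 degrees of freedom.

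| k | n per phase | Power, ICC 0 | Power, ICC 0.10 |
|---|---|---|---|
| 0 | 85 | 82% | 86% |
| 3 | 74.8 | 77% | 81% |
| 5 | 68 | 73% | 77% |

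**The case against.** A reader might infer from point 3 that the second cohort is restricted to course completers while the first holds all 25. The text does not support that. Point 3 repeats point 1, which carries over all 25 at 4 patients each, and the reference to completing the course sets the timing of recruitment. Nothing excludes a partial attender.

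It is also fair to say that the problem is hypothetical. The documents neither report nor forecast any loss of physiotherapists, and nothing in them shows that leavers would have worse patient outcomes. This stands, and it is why the bias is given as a conditional range with no presumed direction. A reader might also suppose a much larger effect, such as leavers' patients faring a full patient-level SD (18 points) worse. Even if exactly the worst physiotherapists left, that gap would need an ICC of about 0.31 (k = 3) or 0.35 (k = 5), and the documents give no basis for such values.

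Finally, the written analysis is paired testing of baseline against 3 months, so this point refines a contrast that the plan has not yet formally specified. That is true, but the sample size rests on that contrast. Once it is written down, it costs nothing extra to write it within physiotherapist.

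**Conclusion.** The concern holds in a limited form. The design intends the same physiotherapists in both phases, but the analysis does not protect that feature, and loss after the first phase acts on one cohort only. If loss is related to outcome, the contrast is biased by physiotherapist mix. In the adverse scenario above, the shift is about 0.4–1.2 points for 3 lost and 0.6–1.9 for 5 lost. On these assumptions it could distort the planned 8-point difference but not produce it. The range rests on assumed ICCs of 0.01–0.10, an assumed number lost, equal patients per physiotherapist, and the worst-outcome physiotherapists being the ones who leave. With no loss, the expected shift from this source is zero.

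**What to change.** In Statistics, state that the pre- versus post-education contrast in 3-month disability is estimated within physiotherapist, with physiotherapist as a fixed effect. Physiotherapists with patients in only one phase then do not contribute to the contrast, so a separate sensitivity analysis that drops them is unnecessary. Report the number of patients per physiotherapist in each phase. This should be fixed before it is known who fails to continue.

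The cost is one or two sentences. The downside is small: patients of single-phase physiotherapists add no information, which gives the power figures tabulated above for 3 or 5 lost. With no loss, power is the same or slightly higher than in the unadjusted comparison, because stable differences between physiotherapists leave the residual variance. The fixed effect addresses physiotherapist mix only. It does not remove other differences between the two calendar periods.

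### The Statistics section tests change from baseline, not the pre- versus post-education difference for which the study is designed and sized

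*Combined protocol and SAP*

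**What the plan says.** The Objective is "To investigate potential changes in patient outcomes following an educational intervention aimed at upskilling physiotherapists". The primary outcome is "Roland Morris Disability Questionnaire 3 months after entering the study".

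Under Schedule of procedures and assessments, point 1 has 25 physiotherapists recruit 4 patients each (100 in total). Point 3 repeats this with a further 100 patients after the course. The two cohorts are therefore different patients treated by the same physiotherapists.

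The Statistics section opens generally: "Statistical analysis will be performed using the appropriate statistical method according to the specific aims investigated". It then becomes specific: "All primary and secondary outcomes will be analysed using paired tests (parametric or non-parametric based on normality), comparing baseline data". The full contrast reads "comparing baseline data and data 3 months after study start". It does not say whether the paired tests are run within each cohort or on all patients pooled.

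The next paragraph sizes the study differently: "we expect to find a 30% group difference in disability in favor of the post-education group". The inputs are "With a mean of 36 (SD 18) pre-intervention and 28 (SD 18) post-intervention", and the conclusion is that "we expect that N=100 participants in each group will be sufficient to achieve an alpha level of 0.05 with a 0.8 power", with 10–15% dropout allowed for.

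**The concern.** The assigned test and the sizing hypothesis are different contrasts, in adjacent paragraphs. A paired test asks whether patients change between baseline and 3 months. The study asks whether patients seen after the course do better than those seen before it. Because the cohorts are different people, no patient-level paired test can answer that.

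Patients may improve through natural course, regression to the mean or usual rehabilitation. A significant paired result therefore does not show that the education made a difference. If the paired results are all that is tested, the study does not test its own question. If a between-cohort comparison is added later, its form (3-month values or change scores, adjusted or not, clustered or not) is not fixed by this plan and could be chosen with the data in view.

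**Working it through.** **1. The plan's own sample size.** Inputs from the Statistics section: means 36 and 28 (difference 8), SD 18, alpha 0.05, power 0.8, dropout 10–15%. Sidedness is not stated; two-sided is assumed.

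n per group = 2 × (1.960 + 0.842)² × 18² / 8² = 2 × 7.85 × 5.0625 ≈ 79.5, so 80 (81 by the t test).

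- With 10% dropout: 81 / 0.90 = 90.
- With 15% dropout: 81 / 0.85 = 95.3, so 96.
- Power of the t test with 100 recruited: 0.843 at 90 completers and 0.821 at 85.

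So 100 per group is sufficient, with a small round-up, for a comparison of two independent groups. These figures ignore clustering by physiotherapist.

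**2. What a paired test would have needed.** SD of change = 18 × √(2(1 − r)). The documents give no correlation r, so a range is assumed. For an 8-point change at 80% power (t test):

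| r (assumed) | SD of change | patients needed |
|---|---|---|
| 0.3 | 21.3 | 58 |
| 0.5 | 18.0 | 42 |
| 0.7 | 13.9 | 26 |

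The stated 100 per group is much closer to the two-sample calculation.

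**3. What the paired tests would show if education had no effect.** This is illustration only, since the documents give neither a usual improvement nor r. Chance that one cohort of 85 completers gives a significant paired test:

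| usual improvement (assumed) | r = 0.3 | r = 0.5 | r = 0.7 |
|---|---|---|---|
| 4 points | 0.402 | 0.526 | 0.744 |
| 8 points | 0.928 | 0.982 | 0.999 |

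Simulation (20,000 runs, 85 per cohort, SD 18, r = 0.5, usual improvement 8 points):

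| true education effect | both paired tests significant | between-cohort test significant |
|---|---|---|
| 0 | 0.966 | 0.051 |
| 8 points | 0.983 | 0.820 |

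With 4 points of usual improvement and no education effect, only the post-education cohort is significant in 0.251 of runs (analytically 0.526 × 0.474 = 0.249). By symmetry, only the pre-education cohort is significant about as often.

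**4. Power of the corrected analysis with clustering.** Assumed: 85 completers per cohort, so m = 85/25 = 3.4 patients per physiotherapist per period. Residual SD = 18 × √(1 − r²). Design effect = 1 + (m − 1) × ICC − m × ICC × c, where c is the share of the physiotherapist effect that persists across periods. With c = 0 the design effect is 1 + 2.4 × 0.05 = 1.12 at ICC 0.05, and 1.24 at ICC 0.10.

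| ICC (assumed) | r (assumed) | power, c = 0 | power, c = 1 |
|---|---|---|---|
| 0.05 | 0.3 | 0.78–0.81 | 0.838 |
| 0.05 | 0.5 | 0.85–0.88 | 0.898 |
| 0.10 | 0.3 | 0.73–0.77 | 0.859 |
| 0.10 | 0.5 | 0.81–0.85 | 0.914 |

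The c = 0 ranges cover the formula at 168, 48 and 24 degrees of freedom, and a simulation with unequal clusters (40,000 runs, 15% random dropout, about 24 degrees of freedom, type I error 0.049–0.050). The c = 1 column comes from that simulation.

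**The case against.** The strongest reply is that the plan is incomplete rather than contradictory. Paired tests can stand beside a between-cohort test, the opening sentence reserves the choice of method, and the sizing paragraph makes the intended contrast plain. The contrast is indeed identifiable, and a test could still be fixed before the data are examined. But the opening sentence names no test, and the specific sentence after it gives every primary and secondary outcome to the paired test. The plan as written still does not test its contrast.

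Pairing by physiotherapist is conceivable. It is not stated, though, and it would compare periods rather than baseline with 3 months.

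Several objections to the figures stand in part:

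- The match to 100 per group is approximate (90–96 after dropout), and 100 is also 25 × 4. The wording, more than the arithmetic, shows that two groups were meant.
- The simulation compares significance verdicts. In its second scenario a reader would see mean changes of 8 and 16 points, but no formal test of that difference is planned.
- Usual improvement, r, ICC and persistence are all assumptions.
- The sizing paragraph says disability without naming the instrument. Applying its figures to the Roland Morris score is a further assumption.

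It is also fair that a detailed mixed model is only one way to repair the gap.

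**Conclusion.** The concern holds and must be fixed. The only test assigned to the primary and secondary outcomes contains no pre- versus post-education contrast. It conflicts with the group difference on which the study is sized. This follows from the text alone; the simulations show the consequence and are not needed for the conclusion.

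On the plan's own inputs, two-sided and ignoring clustering, the planned 100 per cohort supports the missing comparison at 82–84% power. With clustering and no persistence of physiotherapist effects, power is about 80% at ICC 0.05 and r = 0.3, and below 80% at ICC 0.10 and r = 0.3. It is about 0.84 or higher in all four cases if those effects persist fully.

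**What to change.** Replace the paired-test sentence in the Statistics section with text such as:

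> The primary analysis compares the Roland Morris score 3 months after study entry between the post-education and pre-education cohorts. It uses a linear mixed model with cohort as the contrast of interest, baseline score as covariate, and random effects for physiotherapist and physiotherapist-by-period, with Kenward-Roger degrees of freedom. If the model does not converge, the physiotherapist-by-period effect is removed and the physiotherapist effect kept; a variance estimated at zero does not count as non-convergence. The adjusted mean difference is reported with its 95% CI. Secondary outcomes with a baseline value use the same model. Patient satisfaction, for which no baseline is stated, is compared between cohorts at 3 months in a proportional-odds model with a random effect for physiotherapist. Within-cohort paired changes are descriptive. Because the cohorts are sequential and not randomised, the difference is interpreted as an association.

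The essential correction is a named between-cohort comparison; this model is one suitable form. Since the cohorts are not randomised, the sponsor may also pre-specify further covariates from the baseline data already collected.

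The cost is wording, plus recording the treating physiotherapist for each patient. Questionnaires at the start of rehabilitation are already planned. On the plan's own inputs, ignoring clustering, no larger sample is needed. The sponsor should state its assumed ICC and baseline correlation next to the sample size, because power could fall below 80% under the less favourable values.
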